Given the current lack of evidence on particle aerosolization during endoscopy, we plan to conduct a randomized controlled trial utilizing a commercially available particle detector to assess particle suspension in the air during upper endoscopic procedures. We hypothesize that use of an endoscopic patient facemask reduces periprocedural aerosolization during upper endoscopic procedures. Our initial effort will be focused on conducting a pilot trial to assess population variability as no baseline data exists for aerosolization in the general population. We hope to subsequently conduct a larger scale trial to fully test our hypothesis. If an endoscopic facemask significantly reduces aerosolization it could be used to decrease infectious risk to providers while posing minimal risk to the patient and without significantly altering the endoscopic procedure.

Methods

Study Design: Prospective randomized controlled trial

Sample Population

- All patients presenting for an elective upper endoscopic procedure with monitored anesthesia care
- For the pilot trial we plan to recruit 50 total patients, 25 patients in the control arm without a procedural facemask and receiving 2-4 L/min of oxygen via nasal cannula and 25 with a specially designed facemask. An additional 10 patients will be enrolled to account for subject dropout as necessary. Sample size calculation was conducted for the purpose of estimating population variability with a 0.05 level of significance and 0.8 power level. This was done with the assistance of the Department of Quantitative Health Sciences at the Cleveland Clinic
- Inclusion Criteria:
 - All patients undergoing elective upper endoscopic procedures (upper endoscopy, ERCP, endoscopic ultrasound) with monitored anesthesia care at main campus Cleveland Clinic Q3 inpatient endoscopy unit.
- Exclusion Criteria:
 - Any patient requiring endotracheal intubation
 - Pregnant patients
 - Emergency procedures
 - Patients who require use of a facemask before or during the procedure due to medical necessity
 - Patients under the age of 18
 - Non-English speaking individuals
 - Patients unable to provide consent.
 - Any procedure done outside the designated procedure room.
 - If in the opinion of the anesthesiologist, a subject who was randomized to the control arm requires placement of the procedural mask to augment oxygenation, the subject will be removed from the study

Research Procedure:

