 - Any intra-procedural manipulation of the patient's head and neck (ie. head tilt, jaw thrust)
 - Any removal and reinsertion of the endoscope
 - Any opening of the designated procedure room door
 - Any use of the endoscope working channel
 - Peak and mean aerosolized particle counts. This will be obtained during three intervals for six different sizes (0.3 μ m, 0.5 μ m, 1 μ m, 2 μ m, 5 μ m and 10 μ m). The three intervals are: A. A 5-minute baseline period before initiation of sedation. B. Intra-procedurally and C. Post procedurally for 5 minutes, which is defined as beginning after the endoscope is removed.
- Data collected post-procedurally
 - Total procedure duration
 - Total dosage of medications utilized for sedation
 - Use of any reversal agents
 - Peak and mean aerosolized particle counts for 5 minutes after endoscopy completed
- After the patient exits the procedure room no further patient data will be collected
- Post-procedurally patients will follow standard post endoscopy monitoring prior to discharge.

Sample Size Calculation and Data Analysis

Sample size calculation was conducted for the purpose of estimating population variability with a 0.05 level of significance and 0.8 power level. This was done with the assistance of the Department of Quantitative Health Sciences at the Cleveland Clinic.

Data will be described using means (standard deviations) for normally distributed continuous variables, medians [quartiles] for non-normally distributed continuous variables, and frequency (percentage) for categorical variables. Shapiro-Wilks test will be conducted for continuous variables to assess normality. Analysis of variance (ANOVA) or the non-parametric Kruskal-Wallis tests will be used to assess differences in continuous variables. The chi-square test and Fisher's exact test will be used to compare categorical variables as appropriate. A linear mixed model will be used to assess the association between the clinical factors and concentration level of each particle. The mixed model will be used to account for

within subject correlation. All tests will be two-tailed and performed at a significance level of 0.05.

Analyses will be performed using R software

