Particle concentrations for the six sizes measured by the device (0.3 μ m, 0.5 μ m, 1 μ m, 2 μ m, 5 μ m and 10 μ m) will be assessed during three intervals: (1) 5 minute baseline prior to the procedure (2) during the procedure and (3) 5 minutes after endoscope removal. The primary endpoint for the study will be the mean / median concentration of each particle for the three measurement intervals. Our hypothesis is that use of the facemask will significantly decrease aerosolization of all particle sizes during the procedure when compared to controls.

Demographic, procedural and particle concentration data will be placed into a RedCap database, by Drs. [name] and [name]. Additional access to the database will be granted to [name], MS from the department of Quantitative Health Sciences who will be conducting the statistical analysis.

Adverse Events and Data Monitoring Committee (DMC)

This is a minimal risk study. The PI has been involved in procedures which utilized this device without any adverse events. Literature review as well as review of the MAUDE database failed to reveal any instances of complications stemming from the use of this facemask.

Consent

Consent will be obtained by one of the investigators in the pre-procedure area of the endoscopy suite. Patients will be given the option clearly to not participate in the research study while still participating in their planned endoscopic procedure. Subjects deemed not able to consent for the procedure themselves will not be included within the research study. Attached is the proposed consent document.

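### The pilot is meant to measure variability, but no SD on a fixed scale with an interval is planned, and the quoted 0.8 power does not describe its precision

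*Combined protocol and SAP*

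**What the plan says.** Background and Significance describes the study as a "pilot trial to assess population variability as no baseline data exists for aerosolization in the general population", and leaves the definitive test for later: "We hope to subsequently conduct a larger scale trial to fully test our hypothesis".

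The size is 25 patients per arm, with up to 10 more to cover dropout. Sample Population and Sample Size Calculation and Data Analysis justify it with the same sentence: "Sample size calculation was conducted for the purpose of estimating population variability with a 0.05 level of significance and 0.8 power level".

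For the summaries, the latter section says: "Data will be described using means (standard deviations) for normally distributed continuous variables, medians [quartiles] for non-normally distributed continuous variables". The rule that chooses between them is: "Shapiro-Wilks test will be conducted for continuous variables to assess normality". It also plans ANOVA or Kruskal-Wallis tests and a linear mixed model for clinical factors. It does not name the model's variance components as a result to be reported, and it plans no interval for any measure of spread.

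The endpoint and hypothesis follow: "The primary endpoint for the study will be the mean / median concentration of each particle for the three measurement intervals", and "Our hypothesis is that use of the facemask will significantly decrease aerosolization of all particle sizes during the procedure when compared to controls".

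**The concern.** Two things do not match the stated purpose.

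First, a pilot run to estimate variability should commit to one variability estimate, on one scale, with a statement of its uncertainty. Here the measure of spread depends on a test result. One particle size may be reported with an SD on the raw scale and the next with quartiles. Whoever designs the larger trial would then have no common quantity across the six sizes and no indication of how far each could be off. Patient-level data are kept in the study database, so the SD could be computed afterwards, but the scale would then be chosen with the data in view.

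Second, power is the probability that a test rejects under a stated alternative. Attached to an estimation aim, with no test, effect, variance ratio or interval width, the 0.8 says nothing about how well variability will be estimated. Placed near a hypothesis that the mask significantly lowers every particle size, it can be taken for power to detect a mask effect.

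**Working it through.** **1. Can 25 per arm be reproduced?** The documents give a 0.05 level, 0.8 power, 25 per arm and two-tailed tests. They give no effect, SD, variance ratio or target width, so a forward calculation is not possible. Working backwards, several designs fit:

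- Difference in means, normal approximation: n per arm = 2(1.960 + 0.842)² / d². With d = 0.80 SD this is 2 × 7.85 / 0.64 = 24.5, rounded up to 25.
- F test of equal variances, 24 and 24 degrees of freedom: 80% power at an SD ratio of 1.79.
- Precision: upper 95% limit within 25% of the pooled SD, which needs 25 per arm.

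Any sample size fits some criterion once the free quantity is solved for. These results show only that the inputs are absent; none should be attributed to the sponsor.

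**2. What 25 per arm gives for an SD.** Assume approximately normal values on the log scale, with equal variance in the arms. The 95% interval for the SD runs from s√(ν/χ²₀.₉₇₅) to s√(ν/χ²₀.₀₂₅).

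| | ν | Lower factor | Upper factor |
|---|---|---|---|
| Pooled within arms | 48 | √(48/69.02) = 0.83 | √(48/30.75) = 1.25 |
| One arm | 24 | √(24/39.36) = 0.78 | √(24/12.40) = 1.39 |

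For a fixed log-scale difference, the sample size of the later trial scales with the variance. The pooled factors therefore translate into about 0.70 to 1.56 times the size based on the point estimate.

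**3. What 25 per arm gives for one mask comparison.** For a two-sided 0.05 t test with 48 degrees of freedom and noncentrality d√(25/2), power reaches 80% at d = 0.81 SD. At d = 0.5 SD it is 41%.

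**4. How often the summary would switch to quartiles.** The documents give no distribution, so log-normal data are assumed, with n = 25 (the test applied within one arm). The simulated Shapiro-Wilk rejection rates at the 0.05 level are below; repeated runs agreed to within about one percentage point.

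| Assumed log-scale SD | Normality rejected, quartiles reported | Not rejected, raw-scale SD reported |
|---|---|---|
| 0.25 | about 24% | about 76% |
| 0.5 | about 62% | about 38% |
| 0.75 | about 89% | about 11% |

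**5. Does the interval method matter?** Under the same assumption, the nominal 95% chi-square interval for the raw-scale SD in one arm covered the true value about 90%, 77% and 59% of the time at log-scale SDs of 0.25, 0.5 and 0.75. Applied to the logged values, it covered 95% in each case. The factors in step 2 therefore hold on a scale where the data are close to normal, and not on a skewed raw scale.

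**The case against.** The sample-size sentence itself says the purpose is estimation, and Background and Significance leaves the full test to a later trial. A careful reader would not take the 0.8 as power for the mask. Some measure of spread will be reported for every variable, the mixed model yields variance components, and quartiles can be converted to a log-scale SD if log-normality is assumed. The patient-level data remain available. On this view little is lost, and asking what the 0.8 meant is only a request for missing detail.

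Much of this stands, and it limits the weight of the point. It does not remove the mismatch between aim and output. The variance components are not named as results, a conversion from quartiles carries no interval, and a scale chosen later is chosen after seeing the data.

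Two stronger readings are tempting. One is that 50 patients is a miscalculation or too few. The documents do not support this: they set no target against which 25 per arm fails, and a pilot need not be powered for the efficacy question. The other is that the sponsor sized the trial for a mask effect of about 0.8 SD. That value comes only from solving backwards, and other criteria fit equally well.

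The rejection rates also rest on an assumed distribution. If concentrations are close to normal, or so skewed that nearly every size is rejected, the reports would be more uniform, but still without an interval.

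**Conclusion.** The point holds as a gap in analysis specification, not as an arithmetic error, and correcting it is a cheap improvement. The pilot's declared product is a variability estimate, yet the plan lets a normality test choose its form, gives it no interval, and makes a location measure the primary endpoint. Under log-normality with n = 25, between about a quarter and nine tenths of samples would yield quartiles only, over log-scale SDs of 0.25 to 0.75; these SDs are assumptions.

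The phrase "estimating population variability with a 0.05 level of significance and 0.8 power level" does not describe the precision of 25 per arm. On a scale where data are near normal with equal variances, that precision is 0.83 to 1.25 times the pooled SD estimate. Nor should it be read as power for the mask hypothesis, for which a single unadjusted comparison reaches 80% only at about 0.81 SD. The sample size cannot be verified from the documents, which is different from being wrong.

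**What to change.** In Sample Size Calculation and Data Analysis, add an output that does not depend on the normality test. For each particle size, report the between-patient SD of the intra-procedural concentration on the log scale, with a stated rule for zero counts, by arm and pooled within arms, each with a 95% confidence interval. Report also the correlation with the baseline interval, which the larger trial can use in its sizing. If the sponsor keeps another scale, use a bootstrap or other robust interval, because the chi-square interval under-covers with skewed data.

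In Sample Population and in Sample Size Calculation and Data Analysis, state the actual basis of the 0.8, with its test and effect or its target width. If there is none, replace it with wording such as:

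> Assuming approximately normal (log) concentrations with equal variance in the arms, 25 per arm gives a 95% confidence interval for the SD of about 0.83 to 1.25 times the estimate pooled, and 0.78 to 1.39 within one arm. A single unadjusted two-sided 0.05 comparison has 80% power only for about 0.81 SD.

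The cost is a change of wording in two places and one simple analysis of data already collected, with no extra patients or measurements. The drawback is that the stated figure looks less favourable than a bare 0.8.

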Research Protocol

Title: Does Use of a Facemask Reduce the Risk of Aerosolization During Anesthesia Assisted Upper Endoscopic Procedures: A Randomized Controlled Pilot Trial

PI: [name] [name]

Co-Investigators: [name] MD, [name], MS, [name], MD, MS, [name], MS, [name], [name], [name], [name], [name], [name], [name].

Introduction

There is little evidence describing the aerosolization of potentially infectious particles during gastrointestinal endoscopy. Such a phenomenon could potentially place medical staff and patients alike at exposure risk despite the use of personal protective equipment as once aerosolized, microscopic water droplets could remain suspended in the air for hours and represent a potential risk of spread of infectious agents. We propose a randomized controlled pilot trial to assess aerosolization and the potential use of an endoscopic patient facemask to reduce the risk of viral transmission.

Background and Significance

Unfortunately there is a lack of data regarding infectious risk posed to healthcare providers by aerosolization during upper endoscopy. Furthermore, the current COVID-19 pandemic has heightened stress surrounding the danger of potential aerosolizing procedures. While personal protective equipment may reduce some risk, aerosolized particles can remain suspended in the procedural room environment and may lead to transmission despite the use of personal protective equipment. There is only one prospective observational study assessing aerosolization during endoscopy, which used a handheld particle detector in 93 patients undergoing upper endoscopy and found significant increases in particle suspension within the air in the endoscopy procedure room at a distance from the subject where the endoscopist and support staff would be located.

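### The primary summary is left as mean or median, to be settled by a normality check, and no baseline-adjusted analysis is named for the mask comparison

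*Combined protocol and SAP*

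**What the plan says.** All of the analysis text is in Sample Size Calculation and Data Analysis.

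- **Endpoint:** "The primary endpoint for the study will be the mean / median concentration of each particle for the three measurement intervals".
- **Description:** "Data will be described using means (standard deviations) for normally distributed continuous variables, medians [quartiles] for non-normally distributed continuous variables".
- **Normality check:** "Shapiro-Wilks test will be conducted for continuous variables to assess normality". No threshold is given. The text does not say whether the check is pooled, by arm or on residuals.
- **Group tests:** "Analysis of variance (ANOVA) or the non-parametric Kruskal-Wallis tests will be used to assess differences in continuous variables". What decides between the two is not written.
- **Mixed model:** "A linear mixed model will be used to assess the association between the clinical factors and concentration level of each particle". Its purpose is stated as handling within-subject correlation. No outcome scale, covariance structure, arm term or interval term is given.
- **Hypothesis:** "Our hypothesis is that use of the facemask will significantly decrease aerosolization of all particle sizes during the procedure when compared to controls". Tests are two-sided at 0.05.

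Data Collection adds that both peak and mean counts are recorded in each interval, including a 5-minute baseline. Background and Significance gives the pilot's aim as "conducting a pilot trial to assess population variability as no baseline data exists for aerosolization in the general population".

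**The concern.** A mean and a median are different targets. If the data choose between them separately for six sizes and three intervals, the results table can mix quantities that cannot be compared across sizes or between baseline and procedure. There would also be no single effect measure with a confidence interval to carry into the larger trial.

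The second gap affects power more. Each patient's own pre-procedure concentration is measured, and room air plausibly differs from one case to the next. Yet neither ANOVA nor Kruskal-Wallis, as named, uses that reading, and no analysis is designated for the one comparison the hypothesis is about. In a trial of 50 patients, an informative baseline is the cheapest source of precision available.

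**Working it through.** **1. The plan's own figure.** Sample Population gives 25 per arm, and the level and power are 0.05 and 0.8. No effect size, SD or precision target is given, so the 50 cannot be reproduced. Inverting the two-sample formula shows what 25 per arm can detect:

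(1.960 + 0.842) × √(2/25) = 0.79 SD by the normal approximation, or 0.81 SD by the t test.

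The value 0.81 is used below as an assumed effect on the log scale, so that a log-scale t test has 80% power. Distribution, SD and correlation are also assumptions; the documents give none. The log-SDs tried are 0.3, 0.5, 0.7 and 1.0, which make the assumed mask/control ratio exp(−0.81 × log-SD) = 0.78, 0.67, 0.57 and 0.44.

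**2. What the normality gate costs.** Simulation used lognormal data, Shapiro-Wilk on the pooled 50 values at 0.05, then a t test (two-group ANOVA) or Kruskal-Wallis.

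| log-SD | 0.3 | 0.5 | 0.7 | 1.0 |
|---|---|---|---|---|
| Power, gated test | 78% | 78% | 79% | 77% |
| Power, t test on logs | 80% | 80% | 80% | 80% |

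Type I error of the gated test is 4.5-4.9%. Repeat runs gave power within 77-80% and type I error between 4.6% and 5.6%. Applying Shapiro-Wilk to each arm separately gave type I error of 4.7-5.6%.

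**3. How often sizes would be treated differently.** With the pooled check and six equally skewed sizes, different sizes go to different methods in 83%, 31%, 3% and 0% of trials at the four log-SDs. The mixing is commonest where mean and median are closest: the mean/median ratio is exp(log-SD²/2) = 1.05, 1.13, 1.28 and 1.65. With skew that differs across sizes (log-SD 0.3 to 1.0), it occurs in 44-53% of trials.

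**4. What baseline adjustment adds.** On the log scale, ANCOVA reduces the residual SD by √(1 − r²), where r is the baseline-to-procedure correlation. The effective standardized difference is 0.81/√(1 − r²), and the noncentrality is that value × √(25/2), with 47 degrees of freedom.

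| r | √(1 − r²) | Effective difference | Noncentrality | Simulated power |
|---|---|---|---|---|
| 0 | 1.000 | 0.81 | 2.86 | 79% |
| 0.3 | 0.954 | 0.85 | 3.00 | 83% |
| 0.5 | 0.866 | 0.94 | 3.31 | 89% |
| 0.7 | 0.714 | 1.13 | 4.01 | 97% |

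Simulated type I error stays near 5%. Most of the gain over the gated test comes from the baseline term: the unadjusted log-scale t test already has 80%.

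**5. Where the log scale does not help.** Gamma data were given the same coefficients of variation, √(exp(log-SD²) − 1) = 0.31, 0.53, 0.80 and 1.31.

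| Method | CV 0.31 | 0.53 | 0.80 | 1.31 |
|---|---|---|---|---|
| Gated test | 76% | 71% | 60% | 38% |
| Log ANCOVA, r = 0.5 | 87% | 81% | 68% | 39% |
| Log ANCOVA, r = 0.3 | 80% | 72% | 59% | 33% |
| Raw-scale ANCOVA, r = 0.5 | 88% | 84% | 77% | 57% |

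**6. Sparse large sizes.** In simulated low counts with a true ratio of 0.57, log ANCOVA with an offset of 0.5 count, halved and doubled, estimated 0.55-0.60 with 1% zeros, 0.56-0.67 with 13% and 0.65-0.79 with 42%.

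**The case against.** The best defence is that the plan does contain a rule. The description sentence says when a mean and when a median is used, so the endpoint wording can be read as shorthand for that rule, and Kruskal-Wallis already protects against skew. This largely stands. A reader might infer that choosing the test after a normality check invalidates the comparison; step 2 shows that it does not. What remains is that the rule lets the reported quantity change with the data, and that it ignores baseline.

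A reader might also infer that the mixed model is a misspecified primary analysis. Fitted to raw skewed data with only a random intercept, it could lose power, and it could reject too often if concentrations rise in both arms during the procedure. Background and Significance does report that an observational study "found significant increases in particle suspension within the air in the endoscopy procedure room", but gives no size for the rise. The documents assign the mixed model to clinical factors. They do not say that it carries the mask effect, that it is on the raw scale or that it has only a random intercept. Its missing scale, covariance and arm term are therefore missing detail, not an established flaw in the mask comparison.

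A third inference is that quartile summaries would defeat the aim of assessing variability. They would not: the investigators hold the raw data and can compute any SD or correlation. It is only worth naming those quantities in the plan.

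Finally, the log scale is a choice that can lose, as steps 5 and 6 show. That objection stands as a stated downside.

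**Conclusion.** The concern holds as a minor, cheap improvement. The text does not fix one primary summary, does not name the analysis for the mask comparison during the procedure, and leaves the measured baseline out of the group tests it names. The gated rule itself is close to harmless.

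The benefit of changing is about 5, 11 and 19 power points at correlations of 0.3, 0.5 and 0.7 (83, 89 and 97 minus about 78), with no material loss at zero correlation. These figures rest on assumed lognormal data, 25 per arm and an effect of 0.81 log-SD. With gamma-like data, high variability and weak correlation, the gain vanishes or reverses. The case for one pre-specified effect measure does not depend on those assumptions; the size of the power gain does.

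**What to change.** Add to Sample Size Calculation and Data Analysis, for example:

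*For each particle size, the mask effect during the procedure is the mask/control ratio of geometric means with 95% CI, from a linear model of log mean concentration during the procedure on arm and log baseline mean concentration. The interval mean count is used, not the peak. Shapiro-Wilk does not select the analysis; Kruskal-Wallis is a sensitivity analysis. If a mixed model is used for the mask effect, it includes arm, interval and arm-by-interval and does not rely on a random intercept alone. The log-scale SD in each interval and the baseline-to-procedure correlation will be reported for planning the larger trial.*

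State one zero-count offset in advance and repeat the analysis at half and double that offset. A size with many zeros should be reported with the resulting range.

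The cost is wording only, with no extra patients or measurements. The downsides are that effects are read as ratios rather than differences, that the log scale may gain nothing or lose power for gamma-like data with high variability and weak correlation, and that results for sparse large sizes depend on the offset.

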- All patients undergoing an upper endoscopic procedure in the designated procedure room with monitored anesthesia care will be eligible for recruitment into the study once exclusion criteria are applied
- Patients will be randomized to receive an endoscopic procedural facemask or to undergo endoscopy without one at the time of enrollment in the pre-procedure holding area. Control subjects will receive supplemental oxygen (2-4 L/min) via nasal cannula as per our standard protocol. Use of this mask will not affect the risk of the procedure nor change the nature of the patient's endoscopy in any way. An example of this commercially available facemask is pictured below. The mask is currently used in the inpatient endoscopy unit at the main campus of the Cleveland Clinic is selected patients for oxygen delivery.

- In order to collect particle aerosolization data, use of a Met One GT-526S Handheld Particle Counter will be used. This device can detect particles of six different sizes ($0.3\mu\text{m}$, $0.5\mu\text{m}$, $1\mu\text{m}$, $2\mu\text{m}$, $5\mu\text{m}$ and $10\mu\text{m}$). This data can be directly downloaded from the device using the associated Comet software. Device pictured below:

- Endoscopy will be performed in accordance with standard procedures at the Main Campus Cleveland Clinic by either a staff gastroenterologist or a gastroenterology fellow trainee under direct supervision by a staff gastroenterologist.

- The device will be placed in a standardized position 12 inches from the head of the subject on a tripod. The device location will not hinder access to the subject by anesthesia, nursing or gastroenterology staff.

Data Collection:

- Data collected before the patient enters the procedure room:
 - Patient Demographics (age, gender)
 - BMI
 - Upper Endoscopic Procedure Type (ex: esophagogastroduodenoscopy, endoscopic ultrasound, endoscopic retrograde cholangiopancreatography)
 - Patient Mallampati Score
- Data collected in the procedure room prior to start of endoscopy:
 - Patient vitals including BMI and oxygen saturation
 - Patient positioning (left lateral decubitus, supine, prone).
 - Oxygen flow rate being administered by anesthesia staff
 - Number of individuals in the room
 - Peak and mean aerosolized particle counts for 5 minutes prior to endoscopy start
- Data collected during the procedure
 - Any change in supplemental oxygen requirement

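### The between-group tests named for the mask-versus-control comparison do not use the baseline count planned in every patient, and the mixed model names no arm, interval or baseline term; the precision lost is of unknown size

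*Combined protocol and SAP*

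**What the plan says.** All of this is in the combined protocol and SAP. Under Sample Size Calculation and Data Analysis:

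- The hypothesis: "Our hypothesis is that use of the facemask will significantly decrease aerosolization of all particle sizes during the procedure when compared to controls".
- The tests: "Analysis of variance (ANOVA) or the non-parametric Kruskal-Wallis tests will be used to assess differences in continuous variables". No covariate or change score is mentioned.
- The model: "A linear mixed model will be used to assess the association between the clinical factors and concentration level of each particle". Its stated purpose is to allow for within-subject correlation ("The mixed model will be used to account for" that correlation). Its terms are described no further.
- The primary endpoint is the mean or median concentration of each of six particle sizes in each of three intervals: baseline, procedure and post-procedure. No contrast between arms is named.

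The baseline window is worded three ways. Data Collection defines it as "A 5-minute baseline period before initiation of sedation", and its list of pre-endoscopy items has "Peak and mean aerosolized particle counts for 5 minutes prior to endoscopy start". The analysis section has "5 minute baseline prior to the procedure".

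Under Research Procedure, randomisation takes place in the holding area, so it precedes the baseline count. That section also says the mask is already used in the unit, in some patients, to deliver oxygen. The baseline count shares its Data Collection list with "Oxygen flow rate being administered by anesthesia staff". No section says when the mask goes on.

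**The concern.** Particle counts near the patient's head may differ between cases for reasons unrelated to the mask. The plan records the number of people in the room and door openings, for example. A count taken in the same room just before the procedure may capture part of that variation. With 25 patients per arm, whatever baseline explains stays in the error term of an unadjusted ANOVA or Kruskal-Wallis comparison.

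The pilot's stated purpose is to learn about variability before a larger trial. A larger trial that adjusts for baseline would be sized on the residual variance given baseline, which requires rho. The plan does not say that either quantity will be reported.

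Adjustment is not automatically right, however. The baseline count follows randomisation. If the mask is already on and acting in that window, adjusting for the count removes part of the effect being estimated.

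**Working it through.** **The plan's own figure.** The plan gives 50 patients (25 per arm), two-sided 0.05 and power 0.8, but ties the power to estimating variability and gives no difference or SD. The 50 can be neither reproduced nor refuted. Solved backwards, 25 per arm at 80% power corresponds to a difference of 0.81 SD (noncentral t). That is the reference value below.

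**Inputs.** From the documents: n = 25 per arm, two-sided alpha 0.05, power 0.80. Assumed: rho from 0 to 0.8, normal errors (on the log scale if counts are skewed), and equal SDs set to 1. Results are per particle size.

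**Unadjusted.** SE = sqrt(2/25) = 0.283 SD with 48 df. The 95% CI half-width is 2.011 × 0.283 = 0.569 SD. The detectable difference is 0.809 SD.

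**Baseline-adjusted, mask not on at baseline.** SE = sqrt[(2/25)(1 − rho²)(1 + 1/46)] with 47 df. The last factor is the price of estimating the slope.

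| Assumed rho | CI half-width (SD) | Detectable difference (SD) | Power at 0.809 SD |
|---|---|---|---|
| unadjusted | 0.569 | 0.809 | 0.800 |
| 0 | 0.575 | 0.818 | 0.791 |
| 0.15 | 0.569 | 0.809 | 0.800 |
| 0.3 | 0.549 | 0.780 | 0.827 |
| 0.5 | 0.498 | 0.708 | 0.892 |
| 0.7 | 0.411 | 0.584 | 0.972 |
| 0.8 | 0.345 | 0.491 | 0.996 |

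Break-even is at rho of about 0.15. In simulation (40,000 trials per setting, rho 0 to 0.7), the null rejection rate was 0.049 to 0.053 for both analyses, so omitting baseline does not raise the per-test error rate.

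**Mask already acting at baseline.** Let f be the share of the intra-procedural effect already present in the baseline window (assumed). The adjusted estimate then keeps 1 − rho × f of the effect. For example, rho 0.5 and f 0.5 give 1 − 0.25 = 0.75. Simulated power for a true 0.809 SD effect, against about 0.80 unadjusted:

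| rho | f | Share of effect kept | Adjusted power |
|---|---|---|---|
| 0.5 | 0.25 | 0.88 | 0.80 |
| 0.5 | 0.5 | 0.75 | 0.65 |
| 0.5 | 1 | 0.50 | 0.32 |
| 0.7 | 0.25 | 0.83 | 0.89 |
| 0.7 | 0.5 | 0.65 | 0.70 |
| 0.7 | 1 | 0.30 | 0.19 |

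When f is small, power can hold or rise, but the estimate is still attenuated.

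**Consequence for the larger trial.** Take an assumed target of 0.5 SD, 80% power and residual SD sqrt(1 − rho²). The number per arm is 64, 63, 59, 49, 34 or 24 at rho 0, 0.15, 0.3, 0.5, 0.7 or 0.8. An observed rho of 0.5 from 50 patients carries a 95% CI of about 0.25 to 0.68 (Fisher z, SE 1/sqrt(46)), so the interval needs reporting as well as the point value.

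**The case against.** The best defence is that baseline is probably in the plan already. For a given particle size, the three intervals are the only repeated measure described. A mixed model that allows for within-subject correlation would therefore most naturally take baseline as one of its responses. That stands as a likely reading, and it means one cannot say the plan discards baseline. It does not close the gap. With arm, interval and baseline terms unnamed, the mask contrast is undefined. A repeated-measures model with free baseline means in each arm would not by itself deliver the precision gain.

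Second, an unadjusted comparison of randomised arms is valid, and this is a pilot. Both are true. A reader might infer bias or an inflated error rate from the omission; neither follows. (Removing controls who come to need the mask is a separate matter.)

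Third, a reader might see three contradictory baseline windows. The documents do not support that. Data Collection gives an explicit pre-sedation definition, and a pre-sedation window also precedes endoscopy and the procedure. The other wordings are looser and conflict only if one of them means the five minutes immediately before endoscopy. Likewise, the documents do not show that the mask is on at baseline. They leave its timing unstated.

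Fourth, the SD-unit figures assume normality, so they do not describe the Kruskal-Wallis route. That limit stands.

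**Conclusion.** The point holds as a gap in specification with a cost in precision. The named tests leave out baseline, the model does not commit to using it, and the main mask-versus-control contrast is not defined.

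The size cannot be fixed from the documents. Calling the loss minor, or large, would each need a correlation that they do not give. Over the assumed range, adjustment runs from slightly harmful (detectable difference 0.82 against 0.81 SD at rho 0) to a substantial gain (0.49 SD at rho 0.8).

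A reader might also conclude that the gain is available only if the mask is off at baseline. That is too strong: at rho 0.7 with a quarter of the effect already present, adjusted power is 0.89 against 0.80. The estimate then keeps only 83% of the effect, however, so mask status should be settled before adjustment becomes the main analysis.

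These conclusions rest on 25 analysed per arm, normal errors on a suitable scale, equal SDs, and the assumed rho and f.

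**What to change.** 1. State that the baseline window is the pre-sedation one defined in Data Collection, align the looser wording elsewhere, and state whether the mask is on during it.
2. If it is not on, define the main comparison for each particle size as the intra-procedural mask-versus-control difference adjusted for the patient's own baseline count. Use the log scale if counts are skewed, with rank-based covariance analysis as fallback. A three-interval mixed model with arm-by-interval terms, unstructured covariance and a common baseline mean across arms is an equivalent choice. Continue to report the other intervals.
3. Apart from this baseline count, keep factors recorded after randomisation that the mask could affect out of that model.
4. If the mask is on, keep the unadjusted intra-procedural comparison as main and show the adjusted one as a sensitivity analysis only.
5. In either case report the baseline-to-procedure correlation with its confidence interval, and the residual variance.

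No new data are needed, since the baseline count is already planned in every patient. There are two costs. About 1 percentage point of power is lost if rho is 0 (0.791 against 0.800). The main contrast also becomes narrower than the three-interval primary endpoint now stated, which changes the endpoint definition as well as the analysis wording.
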